7. RESEARCH PLAN

7.1 Selection of Subjects

7.1.1. Subject Population.

Patients ages 18 and older presenting to the Emergency department with a complaint of nausea and/or vomiting. All presumed causes of nausea will be included. Inclusion/exclusion criterion is based on safety considerations that were discussed with SAMMC clinical pharmacist. Other considerations are circumstances that altered smell or perception, exogenous emetics, concomitant antiemetic therapy and alcohol exposure. No specimens will be obtained.

7.1.2. Source of Research Material.

Source of Research Material	Conducted for Clinical Purposes(Y/N)	Conducted for Research Purposes
VAS Nausea Score	N	Y
Case Report Form	N	Y

VAS Patient Satisfaction Survey	N	Y
CHCS ad hoc data for all ED patients with nausea or vomiting including those not enrolled in the study for purpose of ruling out selection bias in study population	N	Y

34
 35 **7.1.3. Inclusion and Exclusion Criteria.**

36 Inclusion Criteria:

- 37 (a) ages 18 and older
- 38 (b) complaint of nausea and/or vomiting reported at 3 or above on VRNS at the time of ED triage

39
 70 Exclusion Criteria:

- 71 (a) allergy to isopropyl alcohol or ondansetron
- 72 (b) inability to breathe through nose (e.g., recent upper respiratory infection)
- 73 (c) intake of cefoperazone, disulfiram, or metronidazole within the last 24 hours
- 74 (d) mental status precluding informed consent including intoxication
- 75 (e) known QT-prolongation
- 76 (f) clinical suspicion for serotonin syndrome
- 77 (g) intravenous catheter in place prior to study start
- 78 (h) medications administered since patient arrival to ED (e.g., in triage)
- 79 (i) suspected or known pregnancy

30
 31 **7.1.4. Description of the Recruitment and Prescreening Process.** ED providers and RN triage nursing staff (none of
 32 whom will be study team members) will be apprised of the study inclusion criteria to notify study team members of potential
 33 subjects. Potential subjects will be asked to quantify their nausea on a VNRS (0-10) for the purposes of discerning study
 34 eligibility by triage nurses, the RNs assigned to the patient, or the patient's provider. Efforts will be made to perform this
 35 prescreening process early in the patient's ED course (ideally at the time of triage or initial arrival to treatment room). No
 36 other history, physical exam or other evaluations beyond those normally conducted as the standard of care shall be performed
 37 for the purposes of screening. Triage nurses, the RNs assigned to the patient, the provider assigned will, through their
 38 standard of care assessments and VNRS ascertainment, be able to identify potential subjects (those who meet inclusion
 39 criteria). Triage nurses will notify research staff of potential patients for study enrollment.

30
 31 **7.1.5. Consent Process.** Either the PI or one of the AIs will conduct the informed consent process, which will be
 32 accomplished in the ED while the patient is not receiving active-intervention. The process will take place with the curtain
 33 drawn or door closed to provide the subject appropriate privacy. The subject will have ample opportunity to ask questions of
 34 the investigators and to look over the consent form and HIPAA authorization. The subject will be offered the option of having
 35 a family member present and to be allowed the option of deferring a decision until later into their ED stay. Subjects unable to
 36 provide informed consent for themselves due to diminished decision-making capacity are excluded per paragraph 7.1.3. The
 37 informed consent will notify patients that they will be receiving one of two oral solutions and one of two preparation pads being
 38 studied for the treatment of nausea. They will not be informed of the identity of the substances or that one of the substances
 39 is inert (placebo) given that it is impossible to blind to smell hence we believe that effective blinding to the preparation pad
 40 contents would be impossible without withholding this information. Given the safety profile of these medications, we believe
 41 this research will pose no greater than minimal risk to the participants.

32
 33
 34 **7.1.6. Subject Screening Procedures.** Subjects will be recruited exclusively by the study investigators. Investigators will
 35 approach eligible subjects as identified by either the triage nurse, treating nurses, or treating providers. The recruiting
 36 investigator will inquire as to whether the patient is amenable to possible participation in a study of nausea treatments. If the
 37 patient agrees, the investigator will then verify the potential subject meets inclusion criteria without exclusion through subject
 38 self-report. Agreeable patients will undergo a complete, informed consent process. Data regarding potential subject's age,
 39 sex, and nausea VNRS will be recorded for all patients declining to participate in the study. No personal health information
 40 will be collected on these patients.

13 **7.1.7. Compensation for participation.** No compensation will be provided to the subjects.

14
15 **7.2 Drugs, Dietary Supplements, Biologics, or Devices.**

16
17 **7.2.1 Drugs**

18 Professional Disposable International (PDI) Alcohol prep pads. NDC 10819-3914-2, C69900

19 Professional Disposable International (PDI) Sterile Saline prep pads. C22370

20 Ondansetron Oral Solution 4mg/5ml . NDC 0054-0064-47. 5 ml (4 mg) per subject study dose.

21 Placebo oral solution – 0.25ml of Oral Sweet Sugar Free NDC 0574-0302-16 with 4.75ml of Sterile Water for Irrigation

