56 oral solution. By design, the study will be double-blinded insofar as neither investigators nor subjects will be notified of the
57 identity of the substances they are inhaling or swallowing. We anticipate blinding to scent may be challenging and the

58 study will include a post-study survey to ascertain the extent to which this blinding was achieved. Potential subjects are
59 those presenting to the SAMMC ED with symptoms of nausea and/or vomiting. For the purposes of this study, nausea is
60 defined as the subjective sensation associated with the urge to vomit, and vomiting is defined as the forceful expulsion of
61 gastric contents. Investigators will approach subjects at the time of initial triage and/or while in the waiting room. This will
62 mitigate interruptions in the subject's treatment, possible withdrawals from the control group, and lack of subject interest in
63 the study. Part of the screening process will entail solicitation of nausea on a VNRS scored from 0-10 with those patients
64 reporting scores of 3 or greater eligible for study. Informed consent will be obtained from each subject. Upon enrollment,
65 a study team member will record the patient's date of visit, FMP + sponsor social security number, and date of birth
66 (month, day, year) on the study key which will be maintained in a locked cabinet in the principal investigator's office.
67

68 Regarding blinding, subjects will be informed they will be nasally inhaling one of two common medical preparation pads
69 saturated with different ingredients and taking orally one of two common oral solution substances. Subjects will be
70 allocated to one of three arms: (1) inhaled isopropyl alcohol plus oral ondansetron; (2) inhaled isopropyl alcohol plus oral
71 placebo; (3) inhaled placebo plus oral ondansetron. No subject will receive both inhaled and oral placebo; all subjects will
72 be allocated to at least one therapeutic intervention for nausea. Both investigators and study subjects will be blinded to
73 subject allocation. Randomization will be performed prior to study start with a computer-generated assignment (simple
74 randomization sequence) by an individual not otherwise involved in the study. A copy of the randomization key will be in a
75 sealed envelope and placed in the study file box along with study packets as to be readily available in the ED in case un-

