49 consent, the subject's nausea and pain levels will be recorded initially. For the oral solution, they will be instructed to
50 swallow the oral solution. Receipt of oral solution (ondansetron or placebo) should occur prior to pad inhalation to be
51 followed within 5 minutes by initiation of inhalations from the allocated study pad (normal saline or ISO). For the
52 preparation pads, patients will be instructed to hold the pad approximately 1 inch from their nares and take deep nasal
53 inhalations as needed for nausea relief. Initiation of inhalations will mark time 0 for the study. If a subject is unable to or
54 prefers assistance with either nasal inhalation or oral solution consumption, the patient's nurse will provide any assistance
55 needed. The investigator will remain at arm's length from the patient at all times to avoid detecting prep pad scent.
56 Additionally, investigators will also instruct subjects to avoid any behavior or actions during the study that would indicate
57 which intervention is being used. Examples of behavior to avoid would be verbally describing the scent of the preparation
58 pad or taste of the oral solution. Investigators will not inform subjects which substances are being tested. The
59 preparation pads are commercially prepared single-use pads of ISO for the ISO + oral placebo and the ISO + oral
60 ondansetron study groups and commercially prepared single-use saline pads for the inhaled saline + ondansetron oral
61 solution group that are identical with the exception of the labeling. Both pads will remain in their original packaging. Pain
62 and nausea measurements will be gathered at 0, 10, 20, 30, and 60 minutes and then again hourly up to 5 hours, and
63 then finally at the time the patient's attending physician makes a disposition decision. The patient may withdraw from the
64 study at any time. At any time during the study, a rescue antiemetic drug can be considered by subject request or
65 provider preference. The individual pads will be de-identified, utilizing brown tape over original packaging that tears open

70 with packing as not to reveal manufacturer's labeling. The oral solution packaging will similarly be de-identified. The only
71 scenarios in which a study team member will prompt a provider to consider a rescue anti-emetic is if the patient vomits or
72 if the patient actively requests an alternative medication. A study data form will be completed for each subject by the

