73 study investigators and secured daily in a locked cabinet, along with locked study file box, in the EM APD-R office.

74
75

Assessment	Visit / Follow Up (F/U) Interval Times					
	Initial Presentation	0 min (patient drinks oral solution and starts inhalations)	q10 min until 30 min	1 hour	Hourly until 5 hours	Disposition decision made by patient's attending physician
Study period/interval						
Screening	x					
Informed Consent, discuss Plan, etc.	x					
Allocation according to pre-generated simple randomization sequence	x					
Demographics, History of Present Illness	x					
Medication use	x					
Preparation pad provided		x				
Additional preparation pad offered if needed (up to 10)			x	x	x	
Oral solution provided		x				
Provider contacted for consideration of rescue anti-emetic if vomiting or if subject requests			x	x	x	
Nausea Vomiting VAS		x	x	x	x	x
Episodes of Vomiting		x	x	x	x	x
Pain VAS		x	x	x	x	x
Use of Antiemetic Medication		x	x	x	x	x
Type/Doses of fluids/medications		x	x	x	x	x
Clinical impression						x
Overall Satisfaction VAS						x
Pt perception of pad contents						x
Pt perception of oral solution contents						x
Provider perception of pad contents						x
Provider perception of oral solution contents						x
Investigator perception of pad contents						x
Investigator perception of oral solution contents						x
Summary of adverse events						x

76
77
78
79
30
31

This study concludes at the time of disposition and patient satisfaction will be solicited regardless of outcome.

7.3.1 Collection of Human Biological Specimens. Not applicable.

7.3.1.1 Laboratory evaluations and special precautions. Not applicable.

32
33 **7.3.1.2 Specimen storage.** Not applicable.
34

35 **7.3.2 Data Collection.**

- 36 -Times of subject arrival to ED, bed arrival, study medication receipt (gathered prospectively from order sheet or Essentris)
37 -Patient initial nausea as measured by screening VNRS (0-10): self-reported by the subject.
38 -Demographics: Age in years, sex, FMP/SSN, DOB will be recorded on the study key. Age in years and sex will also be
39 reported on the case report form (CRF). This information will be obtained from the patient's ED medical record labels.
40 -The patient's estimated height, weight, race, smoking history, alcohol use will be recorded on the CRF as self-reported by the
41 patient.
42 -History of Present Illness- Nausea and/or vomiting symptoms of timing, duration, severity, provocation and palliation along

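### Nausea is scored again after consent and at time 0, but no minimum applies there, so patients whose nausea has settled since screening can be allocated, at some cost in power.

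*Combined protocol and SAP*

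**What the plan says.** **Threshold and its timing.** Inclusion criterion (b) in section 7.1.3 reads "b) complaint of nausea and/or vomiting reported at 3 or above on VRNS at the time of ED triage". Section 6 states the same cut-off for screening without a time: "reporting scores of 3 or greater eligible for study". Section 7.1.4 allows the triage nurse, the assigned nurse or the provider to take the score, early in the "ED course (ideally at the time of triage or initial arrival to treatment room".

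**From screening to dosing.** Section 6 intends early contact: "Investigators will approach subjects at the time of initial triage and/or while in the waiting room". Section 7.1.6 adds a check before consent: if the "patient agrees, the investigator will then verify the potential subject meets inclusion criteria without exclusion through subject" self-report. Section 7.1.5 offers the patient "a family member present and to be allowed the option of deferring a decision until later into their ED stay". Under section 6, the study team then enters an order and collects the oral solution from the ED pharmacy against the study number. Under section 7.3, inhalation starts within 5 minutes of the oral dose, and the first inhalation is time 0. No maximum is set for the whole interval.

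**Later nausea scores.** Section 7.3 says that after "consent, the subject's nausea and pain levels will be recorded initially", and it also lists a measurement at 0 minutes. In the assessment table the first nausea VAS stands in the column headed "0 min (patient drinks oral solution and starts inhalations"), and none stands under initial presentation. No minimum is attached to either score.

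**Analysis.** The primary outcome is the 30-minute nausea VAS, compared by an unadjusted two-sample t test (7.4.2, 7.4.3). A multiple regression follows, with covariates not named.

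**The concern.** The trial compares how well two agents relieve nausea that is present. The severity requirement is tied to triage, while treatment starts after referral, consent, ordering and pharmacy collection. Nausea can ease without treatment over that time. A patient who qualified at 3 and has little nausea at dosing has little left to relieve, yet still takes one of the places in the comparison. If there are enough such patients, the observed difference falls below the 20 mm the trial is sized to detect.

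There is also a smaller labelling problem. Section 7.3 does not name the scale of the post-consent score, and the table shows no VAS ahead of the 0-minute column, in which the oral solution is drunk. A reader cannot tell which score is the baseline.

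**Working it through.** **Inputs from section 7.4.1.** SD 28.7 mm (given for change from baseline to 30 minutes), difference 20 mm, two-sided alpha 0.025, power 0.80, 40 per arm. The total is 120 required plus 60 for dropout, giving 180 enrolled, or 60 per arm if the arms are equal.

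**Step 1: the plan's own figure.** n per arm = 2 × [SD × (z for 1 − alpha/2 + z for power) / difference]² = 2 × [28.7 × (2.241 + 0.842) / 20]² = 39.15, rounded up to 40. The stated figure reproduces. By the exact non-central t, power at 40 per arm is 79.5%, and 41 per arm are needed for 80%.

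**Step 2: dilution.** Let f be the share of analysed patients whose nausea has settled by time 0 and in whom the arms do not differ. This is an assumption, because the documents give no figure for f. The expected difference becomes 20 × (1 − f) mm. Power is from the non-central t with non-centrality 20(1 − f) / [28.7 × √(2/n)], two-sided alpha 0.025. For example, f = 10% and n = 40 gives 18 / (28.7 × 0.2236) = 2.805 and power 69.8%.

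| f | Difference (mm) | Power, 40 per arm | Power, 60 per arm |
|---|---|---|---|
| 0% | 20 | 79.5% | 93.8% |
| 5% | 19 | 74.9% | 91.1% |
| 10% | 18 | 69.8% | 87.6% |
| 15% | 17 | 64.2% | 83.4% |
| 20% | 16 | 58.4% | 78.2% |
| 30% | 14 | 46.2% | 65.6% |

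The 40-per-arm column assumes that all 60 extra patients are lost. The 60-per-arm column assumes that none are.

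**Step 3: a smaller spread among settled patients.** Suppose their SD is 10 to 20 mm (assumed). The pooled SD is √[(1 − f) × 28.7² + f × s²]. At f = 10% it is 27.41 mm (s = 10) or 27.95 mm (s = 20), and power at 40 per arm is 74.2% or 72.3%. At f = 20% it is 26.06 or 27.18 mm, and power is 67.7% or 63.6%. This leaves out the extra spread from mixing low scorers with symptomatic patients in a raw 30-minute score, which works the other way.

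**Step 4: where a check could go.** Section 6 puts the consent forms inside the numbered packet and has the oral solution collected against the study number. A check just before swallowing would therefore come after the number has been used, and a patient who fails after consent has already opened a packet. The check has to come at the 7.1.6 verification, or after consent with the forms kept outside the packet.

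**The case against.** The strongest reply is that the plan already limits the problem. Contact is meant to happen at triage or in the waiting room, 7.1.4 allows a score later than triage, and the investigator verifies inclusion before consent. Patients medicated since arrival, or with an intravenous catheter in place, are excluded, so deferring consent until care has begun would often make a patient ineligible. Qualifying on presenting severity is also a defensible choice for undifferentiated ED patients. The enrolment of 180 leaves room for dilution, nausea that is low at time 0 may return by 30 minutes, and 20 mm is not stated as an effect confined to patients who are still nauseated.

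Much of this stands, and it is why the power loss is conditional. It does not close the gap. The criterion verified under 7.1.6 is the triage score, early contact is an intention without a time limit, and the exclusions do not prevent spontaneous settling. The extra 60 patients are budgeted for dropout.

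Two stronger readings are not supported. A reader might infer that nausea is never re-tested before dosing; section 7.3 records it after consent, and only the threshold is missing. A reader might also infer that the baseline is taken after treatment and undermines the primary result. Section 7.3 places the post-consent recording ahead of the oral-solution instructions, and the primary t test uses no baseline.

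**Conclusion.** The point holds as a gap in the entry rule. A patient below 3 at allocation can be enrolled and analysed, and no rule covers that case. Under the assumptions in the working (f of 10% to 20%, no effect in settled patients, equal arms, SD 28.7 mm applied to the 30-minute score), power is about 70% to 58% with 40 analysed per arm and 88% to 78% with 60. With all 60 per arm analysed, power stays at or above 80% up to f of about 18%.

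A reader might infer that dilution will occur, or that it tilts the comparison. The documents support neither. They give no settling rate and no triage-to-dosing interval, and randomisation spreads settled patients over the arms on average. What is at risk is power and the size of the estimated difference. This is a worthwhile, inexpensive improvement and does not invalidate the design.

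**What to change.** 1. Reconcile 7.1.3 with 7.1.4 on when the qualifying VNRS is taken.
2. Have the investigator repeat the VNRS at the 7.1.6 verification and require the existing score of 3 or more before a study number is assigned and the oral solution is ordered. If the repeat is placed after consent, keep the consent forms outside the numbered packet.
3. Label the post-consent nausea score in 7.3 as the pre-dose VAS, show it in the assessment table before the 0-minute column, and name it as the baseline covariate in the planned regression. Adjustment reduces noise but cannot restore an effect in patients with no nausea left to treat, so it does not replace item 2.

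The cost is one repeated question, minor changes to the protocol and forms, a few extra screen failures and slightly slower enrolment. Some settling between the check and the first inhalation will remain, because ordering and pharmacy collection come after it.

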97 be encouraged to take inhalations as frequently and deeply as they feel is necessary to achieve nausea relief. If a subject
98 is unable to or prefers assistance with nasal inhalation or oral solution consumption, the patient's nurse will provide any
99 assistance needed. The investigator will remain at arm's length from the patient at all times to avoid detecting prep pad
100 scent. Additionally, investigators will also instruct subjects to avoid any behavior or actions during the study that would
101 indicate which preparation pad is being used. Examples of behavior to avoid would be verbally describing the scent of the
102 preparation pad or taste of the oral solution.
103

104 The investigators will record their findings on data collection forms. The primary outcome will be nausea as measured on
105 a 10 cm visual analogue scale (VAS) at 30 minutes. This time horizon was selected as ondansetron's labeled use is
106 administration 30 minutes prior to receipt of chemotherapy to treat chemotherapy-related nausea. Nausea measurements
107 will also be collected at 10, 20, 40, 50, and 60 minutes, and then every hour up to 5 hours, then at disposition at which
108 time the patient will provide one final nausea VAS score. The study team member will not be present in the patient's room
109 during the intervals between these evaluations. At the time of each nausea measurement, patients will be offered another
110 preparation pad (up to ten pads). We will notify the patient's treating provider to prompt consideration for treatment with a
111 rescue anti-emetic (such as metoclopramide or promethazine) if the patient vomits or if the patient requests an anti-emetic
112 at any time. At the time of each nausea measurement, a pain score will also be measured on a 10 cm VAS. At the time
113 of final disposition, the patient will provide a satisfaction score on a 10-cm VAS and be asked to indicate his/her belief as
114 to whether the pad was a treatment or placebo and whether the oral solution was a treatment or placebo. Similarly, at

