75 **7.4.3 Data analysis.** In this study, the primary outcome will be evaluated using a two-tailed independent sample student t test.
76 The primary outcome will further be evaluated using a multiple regression model. For secondary outcomes, scale data will be
77 compared using a two-tailed independent sample student t test while categorical data will be compared using a chi-squared
78 test.
79

80 **7.7 Confidentiality.**

31 Protection of Data. Subjects will be assigned a study number upon enrollment in order to facilitate subsequent removal of
32 identifiers upon completion of data analysis. The study number will be recorded on the data collection form and on a study
33 key, which links the study number with the subject's name, FMP, SSN, and DOB. Otherwise patients will be de-identified by
34 eliminating names and collecting only demographic (with ages greater than 89 categorized as "greater than 89"), general
35 description of chief complaint, personal medical, surgical, and medication history; and any other information specific to
36 inclusion and exclusion criteria. The case report forms, signed consent forms, and signed HIPAA authorizations will be stored
37 in a locked cabinet only accessible to the study investigators within the secure EM APD-R office.

38
39 **7.7.1 Certificate of Confidentiality.** N/A.

40 41 **8.0 RISKS/BENEFITS ASSESSMENT**

42
43 **8.1 Risks.** There is a risk to the subjects related to loss of confidentiality. However, this risk is minimized by using a
44 unique study code while collecting study data and limiting access to subject records to the study team. Since all patients
45 will be receiving treatment for nausea (either inhaled isopropyl alcohol, oral ondansetron, or both), we believe the risks of
46 delay in treatment or symptom relief are minimal. Nevertheless, if the treatment to which subjects are allocated is not
47 effective in treating their symptoms, they may experience a delay in rescue therapy and so a delay in symptom relief. We
48 seek to minimize this risk by permitting, subjects to request an antiemetic at any time and to withdraw from the study at
49 any time.

50
51 Additionally, there may be an extremely rare incident of a subject that may have a sensitivity to inhaling ISO. The
52 exclusion criteria were defined to minimize the risks of such reactions by excluding patients recently exposed to
53 medications such as cefoperazone, disulfiram, or metronidazole.

54

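### The exclusion for cefoperazone, disulfiram or metronidazole stops at entry: pads are still offered if one of these drugs is given in the ED afterwards (low priority)

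*Combined protocol and SAP*

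**What the plan says.** - **Purpose of the criterion.** Exclusion (c) in Section 7.1.3 bars "intake of cefoperazone, disulfiram, or metronidazole within the last 24 hours". Section 7.1.1 gives the general basis: "Inclusion/exclusion criterion is based on safety considerations that were discussed with SAMMC clinical pharmacist". Section 8.1 gives the specific one. It says "there may be an extremely rare incident of a subject that may have a sensitivity to inhaling ISO", then that the "exclusion criteria were defined to minimize the risks of such reactions by excluding patients recently exposed to" drugs such as these three.
- **When it is checked.** Under Section 7.1.6 the investigator confirms eligibility once, before consent, from what the subject reports. Exclusion (h) also removes anyone given a drug since arriving in the ED.
- **What happens to pads afterwards.** Section 6 states: "At the time of each nausea measurement, patients will be offered another" preparation pad, with a cap of ten. Besides the 30-minute primary measurement, scores "will also be collected at 10, 20, 40, 50, and 60 minutes, and then every hour up to 5 hours". Section 7.3 and its table use a shorter schedule without 40 and 50 minutes, and qualify the offer as being made if needed.
- **What is recorded.** The 7.3 table has a line for the type and dose of fluids and medications, and 7.3.2 requires times and doses of all ED drugs on the CRF. No action is attached to either record.

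**The concern.** The plan treats recent intake of any of the three drugs as reason enough to keep a patient away from inhaled ISO. That protection operates only at the door. Because exclusion (h) keeps out anyone already medicated in the ED, any ED dose of these drugs to an enrolled subject must come after the only check. From then on the pad-offer rule runs unchanged.

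The people best placed to notice cannot be relied on to do so. Subjects are not told what they are inhaling (7.1.5, 7.3). Treating providers are not told the pad contents either, and are asked to guess them at the end.

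What is at stake is patient safety, on a small scale. The sample size does not depend on it, and the primary outcome at 30 minutes would rarely be touched.

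**Working it through.** **1. Is there a stop rule anywhere?** Setting the relevant sections side by side:

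| Section | What it controls | Acts on a drug given after entry? |
|---|---|---|
| 7.1.3 (c), (h) | Entry | No |
| 7.1.6 | One check at recruitment | No |
| 6 and 7.3, pad offers | Cap of ten; need | No |
| 7.3 table and 7.3.2, drug record | Recording only | No |
| 10.0 | Withdrawal at the subject's wish | Only if the subject acts |
| 6 (key kept in ED), 9.1 (management in ED) | Response to an event | Only after a reaction |

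No section prohibits the three drugs during the study or ties the pad offer to the drug record. This is a gap in the plan; no two sections contradict each other.

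**2. How many subjects are in the ISO arms?** Section 7.4.1 gives 40 per arm, 120 required and 180 enrolled. The 40 reproduces with the normal approximation: 2 × (2.241 + 0.842)² × 28.7² / 20² = 39.2, rounded up to 40. Two of the three arms receive ISO. Assuming equal arms:

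- required: 120 × 2/3 = 80
- enrolled: 180 × 2/3 = 120

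The rate of post-entry use that gives one expected co-exposure is 1/80 = 1.25%, or 1/120 = 0.83%. The documents do not show on which side of this the true rate lies. This counts exposures, not reactions.

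**3. How many pad offers are there after time 0?**

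- Section 7.3: 10, 20, 30, 60 min and 2, 3, 4, 5 h = 8. All 8 fall in table columns that also carry the fluids-and-medications line.
- Section 6: the same plus 40 and 50 min = 10.

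A possible offer at disposition is not counted.

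**4. How many pads could still reach such a subject?** The packet holds ten pads and the first is used at time 0. If every offer is accepted, further pads = min(offers remaining, pads remaining). The time of the drug and the length of stay are assumptions.

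| Drug given just after | Schedule | Pads used | Pads left | 2-hour stay | 5-hour stay |
|---|---|---|---|---|---|
| 30 min | 7.3 | 4 | 6 | min(2, 6) = 2 | min(5, 6) = 5 |
| 30 min | Section 6 | 4 | 6 | min(4, 6) = 4 | min(7, 6) = 6 |
| 60 min | 7.3 | 5 | 5 | min(1, 5) = 1 | min(4, 5) = 4 |
| 60 min | Section 6 | 7 | 3 | min(1, 3) = 1 | min(4, 3) = 3 |

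These are ceilings. Actual use would be lower, because pads are taken according to need.

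**The case against.** The strongest reply is that the documents show no event at risk. They do not say that any of the three drugs is given in this ED, and they do not size the hazard of combining one with inhaled ISO. What they do say points to little harm: sensitivity is described as extremely rare, the inhaled amount as minuscule (9.1) and the study as minimal risk. That stands, and it is why the point is low priority. It does not remove the point, because the plan itself judged the exposure worth excluding at entry.

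A second reply is that exclusion criteria govern entry only, and that criteria (e) and (f), on QT prolongation and serotonin syndrome, have no later stop rule either. But the oral solution is given once, at the start, so there is no later study dose to withhold. Pads are offered repeatedly, so for ISO there is something to stop.

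A third is that further safeguards exist: adverse events recorded at each measurement time, the research monitor and prompt IRB reporting. They do exist, but they respond to harm and do not prevent it.

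Three narrower criticisms stand in part:

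- The break-even rates and pad counts do not measure harm. They bound exposure only, and part of the spread in pad counts comes from the two differing schedules.
- Section 7.3.2 names no source for the ED drug record. If subjects do not know what they were given, a reliable check may mean looking at the chart or orders before each offer.
- Withholding the drug list from providers forgoes the most direct route to avoiding co-exposure. Stopping the pad is still preferable, because the study team controls the pads and clinical treatment is left alone.

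**Conclusion.** The concern holds as a low-priority patient-safety gap. A control that the plan justifies on safety grounds ends at entry, while ISO exposure can continue for up to 5 hours with no matching stop.

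Its size cannot be fixed from the documents. The number affected is probably small, expected harm is small on the protocol's own description, and the effect on the 30-minute primary outcome is negligible. The sample size is unaffected. The conclusion about the missing rule rests on the text alone. The exposure figures rest on equal arms, the assumed drug times and stay lengths, and acceptance of every pad offered.

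**What to change.** Add one sentence to Section 6 and one to Section 7.3:

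- Before each pad offer, the study team completes the scheduled fluids-and-medications check.
- Once cefoperazone, disulfiram or metronidazole has been given, no further pad is offered, in any arm and without unblinding, and the time is recorded.
- All VAS measurements continue and rescue anti-emetics remain available.

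Keep the check within the study team. A drug list handed to providers could hint at the pad contents, and provider belief about the pad is collected.

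**Cost.** The order of one CRF line is fixed. Under 7.3 all 8 offer times already carry the medication check; under the Section 6 schedule it must be added at 40 and 50 minutes. The source of the drug information should be named, and a chart look-up before each offer would add some staff time. A few subjects would lose late pads, which may slightly affect disposition VAS, rescue use and satisfaction.

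**Limit.** A drug given between measurements is found only at the next check, so a pad already in the subject's hand is not covered.
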